Design: We will include COPD subjects with a post-bronchodilator FEV1%predicted below 70% and chronic bronchitis. We will include subjects with at least 2 exacerbations in the last year to identify patients with significant burden due to chronic bronchitis. We will exclude subjects with recent respiratory events or procedures as we want to capture the benefit of HHHFA on chronic, stable COPD participants. Subjects who meet eligibility criteria will be randomized to HHHFA(intervention arm) or usual care (usual care arm). At baseline we will perform measurements in all subjects that include dyspnea, cough, health-related quality of life, and sleep quality questionnaires, spirometry, a 6-minute walk test, and chest CT. The HHHFA device will be provided to participants at the baseline visit.

Protocol: Heated, humidified high-flow air in Chronic Bronchitis

October 8, 2020

HHHFA V4.0

Subjects will use the device during sleep for 6 weeks and return for an end-of-study visit. At the follow-up visit (6 weeks), participants will repeat all baseline evaluations. At the follow-up visit, participants using the HHHFA will be asked whether they want to continue to participate in the sub-study. For participants that have consented to participate in the sub-study, they will use the HHHFA device for an additional 42 weeks. We will follow these participants who continue to use the HHHFA for 42 additional weeks (total 48 weeks) to assess for respiratory exacerbations.

We will compare changes in variables (e.g. FEV1 etc) over time in each treatment group. We will also compare changes in variables over time between groups. To evaluate the effect of treatment, we will use linear mixed effect models controlling for demographics and lung function.

II. Background

COPD is a leading cause of mortality in the U.S.[1] and worldwide[2] and is associated with high morbidity[3] and resource utilization[3], including costs due to clinic visits, chronic therapy, and frequent hospitalizations.[3, 4] COPD patients experience respiratory exacerbations defined as acute worsening of dyspnea, cough, and sputum production.[5]

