- Recent diagnosis (<2 weeks prior to study entry) of pneumonia, respiratory infection, COPD exacerbation, or acute bronchitis requiring antibiotics and new/increased dose of systemic corticosteroids
- Thoracic surgery or another procedure in the last six months that may result in instability of pulmonary status
- Recent medical or surgical history of upper airway disease that may interfere with intervention (e.g., sinus surgery, significant nasal polyps)
- Recent chest illness (trauma, pneumothorax etc).
- Basal skull surgery in the last 6 months
- Open skin ulcer or rash where the nasal cannula will be worn
- Tracheostomy or laryngectomy
- Pregnancy

XI. Schedule of events

After obtaining informed consent, participants will perform a screening pre-bronchodilator and post-bronchodilator spirometry using the EasyOne Spirometer (Zurich, Switzerland) according to American Thoracic Society-European Respiratory Society standards. Participants who meet eligibility criteria will be randomized (2:1) to receive either HHHFA or usual care for 6 weeks. Randomization will be performed using sealed envelopes.

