Baseline visit. After randomization, participants will have baseline measurements and training in the device. Participants will provide information regarding demographics, medical history, COPD history including prior exacerbations, hospitalizations, and pertinent medication use. Weight, height, and vitals will be recorded. Participants will complete Medical Research Council dyspnea scale (MRC),[45] St. George's Respiratory Questionnaire (SGRQ),[46-48] COPD Assessment Test (CAT),[49], Pittsburgh Sleep Quality Index (PSQI),[50], and Cough and Sputum Assessment Questionnaire (CASA-Q).[51] Subsequently, participants will perform a 6-minute walk test follow by an inspiratory and expiratory chest CT. Chest CT will be performed based on quantitative CT lung protocols.[52] TLC and residual volume (RV) will be measured at maximal inspiration and maximal expiration, respectively. We will quantify % emphysema and % gas trapping based on chest CT images. Quantified % emphysema will be defined as the percentage of voxels less than -950 Hounsfield units at TLC. Quantified % gas trapping will be measured at TLC as the percentage of voxels less than -856 Hounsfield units at RV. A parametric response map (PRM) will be constructed to reduce the misclassification of emphysema as gas trapping. Voxels with emphysema on TLC will be eliminated from the voxel count of gas-trapped areas after image matching of TLC and RV images. Airway geometry including Pi10, wall thickness, and visual mucus plugs will also be assessed.[52, 53] Lastly, subjects will receive training and the HHHFA with information materials and a study personnel contact number.

Phone Call at Week 1. Three to seven days after enrollment, a member of the research team will contact the participant to address any concerns or questions regarding the device (device training) and/or the study, and adverse events.

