Follow-up visit (6-weeks). After 6 weeks, participants will return to the CRU with the HHHFA device and perform the same procedures in the same order as at the baseline visit including weight, height, vitals, spirometry, MRC questionnaire, CAT questionnaire, PSQI questionnaire, CASA-Q questionnaire, 6-min walk test, inspiratory and expiratory chest CT. Information regarding changes in medication usage including frequency of rescue inhaler, exacerbation and hospitalizations since the last visit will also be collected. Participants in the HHHFA arm will be asked whether they want to continue to participate in the sub-study that will have them use the HHHFA for an additional 42 weeks. Participants that are not interested in participating in the sub-study, will return the device at the 6 week follow-up visit. Participants interested in participating in the sub-study can ship the device to the research team following their completion of the sub-study that will end at 48-weeks.

Phone Call visit at 12-weeks Only participants in the HHHFA sub-study group will receive a phone call at 12 weeks. Assessment for respiratory exacerbations will be performed.

Protocol: Heated, humidified high-flow air in Chronic Bronchitis

October 8, 2020

HHHFA V4.0

Phone Call visit at 24-weeks. Only participants in the HHHFA sub-study group will receive a phone call at 24 weeks. Assessment for respiratory exacerbations will be performed.

Phone Call visit at 36-weeks. Only participants in the HHHFA sub-study group will receive a phone call at 36 weeks. Assessment for respiratory exacerbations will be performed.

Phone Call visit at 48-weeks. Only participants in the HHHFA sub-study group will receive a phone call at 48 weeks. Assessment for respiratory exacerbations will be performed. Patients will ship the HHHFA device back to the company.

Table 1. Schedule of events summary

[figure not shown]
Activity	Visit 1	Phone Call visit (week 1)	Follow-up visit (6-weeks)	Phone Call visit (12-weeks)	Phone Call visit (24-weeks)	Phone Call visit (36-weeks)	Phone Call visit (48-weeks)
Informed Consent	X						
Screening evaluation and enrollment	X						
Spirometry	X		X				
Demographics and medical history	X		X				
Respiratory condition-related medications only	X		X				
Modified physical exam	X		X				
SaO ₂ at rest	X		X				
Randomization	X						
HHHFA device training and support	X	X	X	X	X	X	X
MRC questionnaire	X		X				
SGRQ Questionnaire	X		X				
CAT score	X		X				
PSQI	X		X				
CASA-Q	X		X				

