- A urine pregnancy test is done on all women of child bearing potential.

XVIII. Statistical Analysis Considerations

Primary outcomes: Sleep quality (PSQI)

Secondary outcomes: Dyspnea (MRC), health-related quality of life (SGRQ and CAT), cough (CASA-Q), lung function (Spirometry), and exercise capacity (6-min walk distance)Chest CT measurements.

Variables will be collected: medical history, comorbidities, MRC, SGRQ, CAT, PSQI, CASA-Q, spirometric variables, 6-min walk distance, Chest CT measurements.

Hypothesis 1: We expect that HHHFA will improve MRC, SGRQ, CAT, PSQI, CASA-Q scores in COPD patients with chronic bronchitis. It will also increase FEV1, and distance covered in a 6-minute walk test.

Hypothesis 2: We anticipate that HHHFA will reduce air trapping and hyperinflation.

Decrease in air trapping and hyperinflation can explain the improvement in respiratory symptoms, lung function, and exercise capacity. The putative mechanism of that is that HHHFA improves airway clearance.

Statistical considerations and power calculation. Prior studies have shown that HHHFA improves dyspnea, quality of life, and lung function in patients with COPD and daily sputum production. HHHFA has not been shown to improve quality of sleep. A prior study has shown that the average of PSQI in COPD patients with FEV1%predicted above 50% is 9.3 ± 3.8 (SD).[54] To achieve a power of 80% at a 2-sided 5% level of significance to detect a clinically significant improvement in PSQI (below 5), we need a sample size at least 27 subjects enrolling ratio of 2:1(HHHFA: usual care). To account for an increased rate of attrition, our goal will be a sample of 30.

Statistical analysis. We will compare variables (e.g. MRC score, FEV1) between baseline and 6-week visits and changes over time in each group. We will use Fisher's exact test for categorical variables and paired t-test or Wilcoxon signed-rank test for normal and non-normal continuous variables, respectively. We will also compare changes in those variables (e.g. change in FEV1 between baseline and 6-week visits) between groups. We will use Fisher's exact test for categorical variables and t-test or Wilcoxon rank sum test for normal and non-normal continuous variables, respectively. To evaluate the effect of treatment, we will use linear mixed-effect models controlling for demographics and lung function.

Statistical analysis will be performed using SAS, version 9.4 and R statistical software (<http://www.r-project.org/>).

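### The within-arm baseline-to-6-week rule names Fisher's exact test, an unpaired test, for categorical variables; the reach is narrow and may be nil

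*Protocol*

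**What the plan says.** The statistical analysis paragraph of protocol section XVIII sets out two comparisons.

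- **Within arm:** "We will compare variables (e.g. MRC score, FEV1) between baseline and 6-week visits and changes over time in each group". The Design paragraph of section I states the same intention: "We will compare changes in variables (e.g. FEV1 etc) over time in each treatment group". The tests assigned are: "We will use Fisher's exact test for categorical variables and paired t-test or Wilcoxon signed-rank test for normal and non-normal continuous variables, respectively".
- **Between arms:** "We will also compare changes in those variables (e.g. change in FEV1 between baseline and 6-week visits) between groups". Here the continuous tests become the ordinary t-test or the rank-sum test, and Fisher's exact test is named again for categorical variables.

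Linear mixed-effect models are then to evaluate the treatment effect. The SAP plans only a between-group rank-sum test on changes in PSQI, CAT and 6-minute walk; it has no within-arm test and no categorical test. Neither document names a paired test for categorical data.

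The variables are listed without saying which are categorical: "Variables will be collected: medical history, comorbidities, MRC, SGRQ, CAT, PSQI, CASA-Q, spirometric variables, 6-min walk distance, Chest CT measurements". Section XI adds, for the CT, "Airway geometry including Pi10, wall thickness, and visual mucus plugs will also be assessed", with no scoring given. For the 6-week visit it adds: "Information regarding changes in medication usage including frequency of rescue inhaler, exacerbation and hospitalizations since the last visit will also be collected".

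**The concern.** When section XVIII moves from the within-arm to the between-arm comparison, it switches the continuous tests from paired to unpaired. The categorical test stays the same. Fisher's exact test suits the second comparison, where the arms are independent. It does not suit the first, where each participant contributes to both visits.

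If a variable were handled as categories, the within-arm p-value would compare two sets of counts as though they came from different people. It would take no account of who improved and who worsened. At stake are within-arm p-values for secondary or descriptive variables, not the comparison of treatments.

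**Working it through.** **Which variables the clause could reach.** PSQI, SGRQ, CAT, CASA-Q, spirometry, walk distance and the quantitative CT measures are scores or continuous, so they go to the paired t-test or signed-rank test. Three candidates remain:

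- MRC, if treated as a grade. Section XVIII calls it a score and gives it beside FEV1 as an example, so it may already go to the signed-rank test.
- Visual mucus plugs, if scored in categories. The scoring is not stated.
- Medication use, which is recorded but is not in section XVIII's list of outcomes or variables.

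**Inputs.** The protocol's target is 30, and "Participants who meet eligibility criteria will be randomized (2:1) to receive either HHHFA or usual care for 6 weeks", which gives arms of 20 and 10. The level is two-sided 5%. The documents give no categorical proportions or within-person correlations, so those below are assumptions. The table assumed is visit (two rows) by category.

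**The plan's own figure.** The only stated design figure is the 27 for PSQI. The normal approximation with difference 9.3 − 5 = 4.3 and SD 3.8 gives 9.2 + 18.4 = 27.6, close to it. It does not use the categorical rule and does not change.

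**Why the direction is conservative.** Let p1 and p2 be the proportions at the two visits and p11 the proportion positive at both. Then

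Var(difference) = [p1(1 − p1) + p2(1 − p2) − 2(p11 − p1·p2)] / n.

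Treating the visits as independent drops the last term. With p1 = p2 = 0.5 and correlation 0.5, p11 − p1·p2 = 0.5 × 0.25 = 0.125. The true variance is then (0.50 − 0.25)/n = 0.25/n, against 0.50/n under independence.

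**Rejection rates with no true change** (exact multinomial enumeration, prevalence 0.5):

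| Test | Correlation 0 | 0.25 | 0.5 | 0.6 |
|---|---|---|---|---|
| Fisher, n = 20 | 2.0% | 0.8% | 0.2% | 0.06% |
| Exact McNemar, n = 20 | 2.3% | 1.8% | 0.9% | 0.5% |
| Mid-P McNemar, n = 20 | 4.2% | 3.8% | 2.6% | 1.7% |
| Fisher, n = 10 | 1.28% | 0.45% | 0.08% | 0.03% |
| Exact McNemar, n = 10 | 0.90% | 0.34% | 0.06% | 0.02% |

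At prevalence 0.3 and n = 20, Fisher gives 2.5 / 1.0 / 0.2 / 0.08%. Fisher never exceeds 5% in these cases. At n = 10 exact McNemar is slightly more conservative still.

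**Power with real change.** Cells are yes-yes / yes-no / no-yes / no-no.

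- 0.30/0.40/0.10/0.20, n = 20: Fisher 34%, exact McNemar 37%. The correlation is 0.02/√(0.21 × 0.24) ≈ 0.09.
- 0.30/0.35/0.02/0.33, n = 20: Fisher 39%, exact McNemar 62%. The correlation is 0.092/√(0.2275 × 0.2176) ≈ 0.41.
- The second set of cells at n = 10: Fisher 9.5%, exact McNemar 8.5%.

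**What is lost when only the margins are used.** Suppose 12 of 20 are positive at baseline and 6 of 20 at 6 weeks. Fisher gives p = 0.111 however the change came about.

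- 6 improve, 0 worsen: exact McNemar 2 × (1/2)^6 = 0.031.
- 12 improve, 6 worsen: exact McNemar 0.238.

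**Why mid-P in small arms.** If all changes go one way, exact McNemar gives 2 × (1/2)^5 = 0.0625 with five changers, so it needs six to reach 5%. Mid-P subtracts half the two-sided tail, 0.0625 − 0.03125 = 0.031, so five are enough.

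**The case against.** The strongest defence is that no analysis is shown to be affected. Nothing is declared categorical, the clause may be generic wording, and the treatment comparison rests on other tests. A within-arm p-value in a 30-person pilot could not establish efficacy whichever test produced it. All of this stands, and it keeps the point minor. It does not make the rule right: the clause is in the plan and names the wrong kind of test for paired data.

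A reader might infer three stronger things that do not hold.

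- **That false positives are inflated.** This would follow if Fisher's test were run on the baseline-by-6-week cross-table, where it tests association between visits, not change. With no true change, prevalence 0.5, correlation 0.6 and n = 20, it would reject 67% of the time. If 10 of 20 were positive at both visits and nobody changed, p would be 0.00001. But section XVIII speaks of comparing variables between visits, which points to a visit-by-category table. Nothing in the documents suggests the cross-table, so these figures do not measure the plan's error.
- **That the natural table gives an invalid test.** With non-negative correlation its false-positive rate stayed below 5%. The cost is over-conservatism and possible loss of power. Negative correlation was not examined.
- **That McNemar always does better.** It does not with 10 in the arm, and in one of the scenarios with 20 the gain is only about 3 points.

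**Conclusion.** The point holds in a narrow form and is minor. The within-arm rule assigns an unpaired test to paired categorical data, and neither document supplies a paired one. Whether any variable falls under it is not stated.

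If one does, Fisher's test on the visit-by-category table ignores who changed. With non-negative within-person correlation it errs towards missing change in the arm of 20, by an amount that ranged from trivial to substantial across the assumed cells. In the arm of 10 there is no power to recover by moving to exact McNemar. The size therefore rests wholly on assumed proportions and correlations.

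A reader should not infer that the primary result is in doubt. The PSQI comparison, the sample size, the between-group tests, the mixed models and the SAP's rank-sum tests do not use this rule.

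**What to change.** In the within-arm sentence of section XVIII, replace Fisher's exact test with:

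- McNemar's test for binary variables, preferably mid-P at these arm sizes, with the version stated in advance;
- the Wilcoxon signed-rank test for ordered grades such as MRC;
- a marginal-homogeneity test for any unordered variable with more than two categories.

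Keep Fisher's exact test for the between-group comparison. State that the baseline-by-6-week cross-table will not be tested with Fisher's test. List the variables handled as categorical and say how visual mucus plugs are scored. If the list is empty, delete the categorical clause from the within-arm sentence.

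The cost is one revised sentence and a short list. Data collection, sample size, primary outcome and between-group analysis do not change.

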## **Cover Page for Statistical Analysis Plan**

Sponsor-Investigator:	[name]
NCT Number:	NCT03959982
Unique Protocol ID:	201905817
Official Title:	The Effect of Heated, Humidified High-flow Air in COPD Patients With Chronic Bronchitis
Date of Document:	01 July 2019

Assessment of the effectiveness of the intervention by assessing the change in the PSQI, CAT, and the 6-minute walk from enrollment to the 6-week visit. The Wilcoxon rank-sum test will be used to compare changes in PSQI, CAT, and the 6-minute walk test from enrollment to the 6-week visit between the intervention and the control group. The Wilcoxon rank-sum test will be used because the dependent variables will most likely not follow normal distribution.

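### Two analyses are named for the treatment effect on PSQI, neither is designated as primary, and neither is stated to adjust for baseline PSQI

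*SAP*

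**What the plan says.** Section XVIII of the protocol lists sleep quality by PSQI as the only primary outcome. PSQI is completed at the baseline visit (Section XI) and again at 6 weeks, where the visit list includes "CAT questionnaire, PSQI questionnaire, CASA-Q questionnaire".

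The SAP is a single paragraph dated 1 July 2019. It sets out "Assessment of the effectiveness of the intervention by assessing the change in the PSQI, CAT, and the 6-minute walk" from enrolment to 6 weeks, and then: "The Wilcoxon rank-sum test will be used to compare changes in PSQI, CAT, and the 6-minute walk test from enrollment to the 6-week visit". The comparison is of the two arms. Its reason is that "the dependent variables will most likely not follow normal distribution". No covariate is mentioned.

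The protocol is dated 8 October 2020. Section XVIII first compares changes between groups by a t-test or, for non-normal variables, a Wilcoxon rank-sum test. It then adds: "To evaluate the effect of treatment, we will use linear mixed-effect models controlling for demographics and lung function". The design text of Section I carries the same sentence. The model's outcome vector, time terms and random effects are not given, and lung function is not marked as baseline.

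Neither document refers to the other, and no rule of precedence is stated.

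**The concern.** Each document ties the assessment of the treatment to a different analysis. The SAP links effectiveness to an unadjusted rank test on change. The later protocol links the effect of treatment to a covariate-adjusted model. With about 27 patients the two can give different verdicts on the same data, and a reader could not then say what the primary result is.

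The second issue is efficiency. A change score uses baseline PSQI, but with its coefficient fixed at 1. Adjusting for baseline PSQI lets the data set that coefficient, which usually gives a more precise comparison in a small trial. The value is already collected, but neither document enters it as a covariate.

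The third is the model's covariates. FEV1 is itself an outcome that Section XVIII expects treatment to raise. If the lung-function covariate were the 6-week value, adjusting for it could remove part of the effect being estimated.

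**Working it through.** **Inputs from Section XVIII.** Mean PSQI 9.3, SD 3.8 (cross-sectional); target below 5, so an effect of 9.3 − 5 = 4.3 (inferred); two-sided 5%; 80% power; 27 patients at 2:1, that is 18 and 9; 30 enrolled. **Assumed, because the documents do not give them:** the baseline to week-6 correlation ρ (0.3, 0.5, 0.7), the error shape, and a 0 to 21 score range.

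**1. The plan's own figure.** Control arm = (1 + 1/2) × [3.8 × (1.960 + 0.842) / 4.3]² = 9.19, so the total is 3 × 9.19 = 27.6. The stated 27 is reproduced. At 18:9 the normal formula gives 79.2% power and the exact t-test 75.9%. A small part of any shortfall from 80% is therefore not due to the choice of analysis.

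**2. What the SD means for each analysis.** SD of change = 3.8 × √[2(1 − ρ)]. SD after baseline adjustment = 3.8 × √(1 − ρ²). The ratio of variances, adjusted to change, is (1 + ρ)/2.

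| ρ | SD, change | Total N | SD, adjusted | Total N | Variance ratio |
|---|---|---|---|---|---|
| 0.3 | 4.50 | 38.6 | 3.62 | 25.1 | 0.65 |
| 0.5 | 3.80 | 27.6 | 3.29 | 20.7 | 0.75 |
| 0.7 | 2.94 | 16.6 | 2.71 | 14.1 | 0.85 |

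The plan's SD of 3.8 is the SD of change only if ρ = 0.5.

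**3. Simulated power at effect 4.3, 18:9.** The comparison is the rank-sum test on change against rank-based ANCOVA (Quade: ranks of week-6 PSQI regressed on ranks of baseline PSQI, residuals compared by arm). Scores are rounded. There are 20,000 trials per cell, with any non-normal error at week 6 only.

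| Error shape | ρ = 0.3 | ρ = 0.5 | ρ = 0.7 |
|---|---|---|---|
| Near-normal | 57 vs 75% | 70 vs 82% | 89 vs 92% |
| Moderate skew | 62 vs 85% | 77 vs 89% | 94 vs 95% |
| Strong skew | 78 vs 98% | 93 vs 98% | 99.2 vs 98.6% |
| Heavy tails | 69 vs 91% | 84 vs 93% | 97 vs 97% |

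Giving both visits the same error shape (10,000 trials per cell) shrinks the gain:
- Strong skew: 87.5 vs 95.5% at 0.3 and 93.8 vs 95.7% at 0.5.
- Heavy tails: 75.3 vs 87.3% at 0.3 and 85.0 vs 89.8% at 0.5.

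Across both designs the gain is about 7 to 23 points at 0.3, 2 to 12 at 0.5, and −0.6 to +3 at 0.7. With near-normal scores, the rank-sum test reaches 80% power at a correlation of about 0.60 and the adjusted rank test at about 0.46.

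**4. Type I error of each test alone** (non-normal error at week 6 only): rank-sum 4.3 to 4.8%, t-test on change 4.6 to 5.1%, linear ANCOVA 4.3 to 5.0%, Quade 4.8 to 5.4%.

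**5. What the mixed model could be.** With an arm-by-time term, demographics and lung function as main effects, and complete data, its estimate equals the difference in mean change. In 150 simulated trials the two agreed to rounding error, so those covariates do not alter the comparison. With a common baseline mean the model is close to ANCOVA. The protocol does not say which is meant.

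**6. Opposite verdicts at effect 4.3.** Rank-sum against a t-test on change: about 4 to 12% of trials. Rank-sum against linear ANCOVA: about 4 to 27%. These two analyses stand in for the two readings in step 5. The protocol's own model, with its covariates, was not simulated for this.

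**The case against.** The strongest reply is that the gap is narrow. The SAP names one test for PSQI and gives a reason, and Section XVIII lists the same test for non-normal variables, so only the mixed model's role is open. That is fair as far as it goes. But the protocol is the later document, and it attaches the phrase about evaluating the treatment effect to the model, so the SAP alone does not settle the matter.

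It can also be said that baseline adjustment by ranks is a preference. That stands in part. The rank-sum test on change is valid, and the essential step is to designate one method.

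The power gain depends on unknowns and is not universal. At effect 3.0 with strong skew at both visits it is nil at correlation 0.5 (77.9 vs 77.9%), and at 0.7 Quade is about 4 to 5.5 points worse (89.4 vs 83.9% in one run). At 0.8 the gain is gone.

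Two stronger readings are tempting. One is that the SAP's test inflates the false-positive rate; step 4 shows that it does not. The other is that the sponsor would report whichever analysis is significant; no passage proposes this.

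**Conclusion.** The point holds as a should-fix, not as a failure of validity. Two analyses are each presented as the assessment of treatment on the sole primary outcome, nothing ranks them, and baseline PSQI is not named as a covariate. The ambiguity does not depend on any assumption.

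The size of the power loss does. It rests on the inferred effect of 4.3, the cross-sectional SD of 3.8, 18:9 allocation, and an assumed correlation and error shape. On that footing it runs from substantial at a correlation of 0.3 to nothing at 0.7, with small reversals beyond. A reader might infer that the rank-based ANCOVA is the only right choice, or that the rank-sum test ignores baseline PSQI. Neither follows: linear ANCOVA is also sound, and a change score does contain the baseline value.

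**What to change.** In both the SAP and Section XVIII, designate one primary PSQI analysis. Suggested text: *The primary analysis compares 6-week PSQI by arm, adjusting for baseline PSQI, using rank-based ANCOVA (Quade) at the two-sided 5% level; this analysis alone determines the primary result. The rank-sum test on change and the mixed model are supportive.* List the mixed model's outcome, time terms, random effects and covariates, and write *baseline* before lung function.

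The rank-based version fits the SAP's expectation of non-normality. Linear ANCOVA is an acceptable alternative: it gives the test, estimate and confidence interval from one analysis, with about 3 points more power than Quade if scores are near-normal (78, 85 and 95% against 75, 82 and 92%).

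The cost is wording only; no visit or measurement is added. The main drawback is that Quade gives no effect estimate of its own. If linear ANCOVA supplies the interval while Quade decides, the two disagree in about 3 to 11% of trials at effect 4.3 and 8 to 23% at effect 3.0, so the text must say which governs. If the sponsor prefers to keep the rank-sum test on change as primary, one sentence in both documents resolves the ambiguity, with the possible power loss shown above.
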